**ACCELEROMETER MOTION TO MEASURE MUSCLE FATIGUE IN CRITICALLY ILL
PATIENTS**

NCT04166630

Date: May 27, 2019

IRB00109793

1. Full title: Accelerometer motion to measure muscle fatigue in critically ill patients

Short title: ICU Acquired Weakness

Principal Investigator: [name], MPH

Co-Investigators: [name]
[name]

Updated Draft Date: May 27, 2019

2. Introduction and background

The primary purpose of this study is to develop a procedure to identify intensive care unit (ICU) acquired weakness. This condition occurs in a subset of people admitted into the ICU, and is associated with a 30% increased risk of death before discharge from the ICU.¹ There are currently major limitations in the ability to diagnose ICU acquired weakness, making it difficult to study.² The goal is to develop a non-invasive test that can be administered to both responsive and non-responsive patients. The current proposal will focus on replicating the results of previous research using motion detecting accelerometers to measure fatigue in human skeletal muscles (Willingham and McCully). This study is designed to test out the procedures in patients who have been transferred from the ICU to a lower level of care so that follow-on studies can be designed to help mitigate this condition in the ICU.

3. Objectives

Objective 1: To identify patterns of muscle fatigue that are distinct for patients with ICU acquired weakness

Objective 2: To identify differences in accelerometer data that appear only in the ICU acquired weakness group for later use as diagnostic criteria.

Objective 3: To develop a diagnostic tool for identifying ICU acquired weakness earlier in the patient's care.

The procedures outlined in this study will advance this objective by providing data that can be analyzed based on whether the subjects have ICU acquired weakness or not based on the current testing procedures.

4. Study Design and Methods

Subjects will undergo a clinical strength assessments to classify them based on whether they test positive for ICU acquired weakness. Manual muscle testing will be performed based on the medical research council (MRC) score. A score of < 48 will classify the subject was having ICU acquired weakness placing them in the "weak" group. Subjects with scores exceeding 48 will be placed into the "not weak" group.

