Potential subjects will be approached regarding participation in this study. They will be provided with a written consent form, and allowed adequate time to read the form. After reading, they will

be given a chance to ask questions. If they decide to participate, they will be asked to sign the consent form.

Subjects will then be asked to fill out a health history form. The subjects will then be escorted to a clinical electrical stimulator. We plan to test a variety of skeletal muscles to ensure mastery of the technique. Conductive electrodes will be on the skin at each end of the tested muscle(s). Each subject will have two target muscle groups tested (extensor carpi radialis longus, and tibialis anterior). Each muscle will be stimulated at three separate stimulation frequencies (2 Hz, 4 Hz, and 6Hz) over 3 minutes each, for a total of 9 minutes of stimulation per muscle. The clinical electrical stimulator will then deliver mild electrical stimulations to the muscle (20-100 mA). This intensity of stimulation typically produces only mild discomfort typical of muscle contraction. The clinical stimulator has a maximum output of 110 mA, phase duration 1,000 microseconds, 250 Hz. Any stimulation delivering 25 microcoulombs or higher cannot travel through the thorax because of the risk of cardiac arrhythmias. All stimulations applied in this study will be below this threshold. The stimulation frequencies listed above will be within this safety margin.

The accelerometer used throughout the study will be an Axivity AX3 wireless accelerometer. It will be placed on the muscle belly using double sided tape between the two stimulating electrodes.

Fatigue will be defined as a drop in acceleration from peak acceleration. This will be measured using a triaxial accelerometer over 3 separate stimulation frequencies for a total of 9 minutes of testing per muscle. The device will record 2,160 individual muscle twitches. The highest acceleration over a single muscle twitch will be used as the peak acceleration. The data will then be normalized to this peak acceleration to quantify the percentage of maximal acceleration of each twitch.

The electronic stimulator is currently FDA approved for use in clinical patients so a device determination is not being requested. The accelerometer is passively recording accelerations, with no energy input to the patient. The FDA currently states the following as approved uses for clinical electrical stimulators:

INDICATIONS FOR USE

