Data storage: Strict patient confidentiality will be maintained. Data other than the health history forms will be collected via a triaxial accelerometer and downloaded directly to a Georgia State University computer. This data will be stored on the computer and backed up to a digital storage device that is locked inside filing cabinet inside a locked office. Only the researchers listed on this application will have access to the data. Following the completion of this study, data will be maintained on a university computer. Any paper records will be stored in the manner listed above. All patient information will be de-identified prior to post-study analysis.

5. Participant selection

Requested Sample Size: 150 (extra 50 to account for subject drop outs)

Inclusion criteria:

1. Patients ≥ 18 years of age
2. Patients transferred from the ICU to a lower level of care within the past 7 days
3. Mechanical ventilation for greater than 7 days while in the ICU
4. Ability to understand English and provide written consent

Exclusion criteria:

1. Vulnerable populations including: patients who are pregnant or prisoners
2. Patients who are unable to understand English or provide written consent

Subject recruitment plan:

Screening for eligibility: Targeted patients will include those recently transferred from the ICU to a lower level of care within the hospital. Following routine care, patient records will be reviewed and patients will be asked if they are interested in joining this study and if they meet the aforementioned inclusion and exclusion criteria.

Withdrawal from study: Formal removal from the study can be done by contacting any of the individuals overseeing the study or members of the individual's normal care team at Grady. This

can be done at any time without affecting the patient's ability to obtain routine follow-up care from the post-op clinic or care staff.

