Informed consent: Consent will be obtained from patients by a trained research assistant or trained member of the study staff. As mentioned above, patients will be identified as meeting inclusion criteria at the time of transfer from the ICU. If they are eligible, the research assistant will approach them with the opportunity of enrolling in the study. At the time, all potential risks, benefits, and procedures related to participating in the study will be explained as described on the informed consent form. The patients will be given the attached informed consent form and, in the case that they sign it, will begin the on-boarding process for enrollment. All patients have the option to avoid enrollment into the study and can end participation in the study at any time, as described above. Patients will be randomly selected and enrolled by research assistants, rather than directly by the principal investigator, minimizing the risk of coercion.

6. Statistical Analysis

Data will be split into 2 groups (weak vs non-weak) based on clinical strength assessment scores. A 2 factor ANOVA will be used to compare peak acceleration, time to peak acceleration, end acceleration, and fatigue ratio based on group (weak vs non-weak) and stimulation frequency (2 Hz, 4 Hz, 6 Hz). We are collecting 9 minutes of accelerometer data for each muscle, and MRC scores for each subject. A post-hoc analysis with Bonferroni correction will be used to identify where differences occur.

7. Adverse event reporting

The probability of adverse events remains extremely low given the nature of this intervention, but patients can report all events directly to the study staff. Depending on the nature of the event, the individual's participation in the study may be terminated. In the case of a data leak or HIPAA violation, the study staff will jointly address the nature of the leak and determine if any PHI has been leaked. Beyond this, standard HIPAA reporting guidelines will be followed.

8. Data and Safety Monitoring Plan

No personally identifiable (PI) information will be shared with anyone outside of the research team or patient's care team. Any data shared following completion of the study will be de-identified prior to use, protecting the patients' PHI and abiding by the HIPAA Privacy Rules. The only foreseeable disclosure of data beyond the study is in the case of publication of data.

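### Holm's method on the three same-frequency weak vs non-weak contrasts would improve on the unrestricted Bonferroni post-hoc step

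*Combined protocol and SAP*

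**What the plan says.** Section 6 names the test and the outcomes: "A 2 factor ANOVA will be used to compare peak acceleration, time to peak acceleration, end acceleration, and fatigue ratio". The multiplicity provision for this analysis is the closing sentence of that section: "A post-hoc analysis with Bonferroni correction will be used to identify where differences occur". No comparisons are listed, no divisor is given, and no alpha is stated. The model has two factors, one with two levels and one with three: "based on group (weak vs non-weak) and stimulation frequency (2 Hz, 4 Hz, 6 Hz").

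The objectives in Section 3 that the analysis serves are "To identify patterns of muscle fatigue that are distinct for patients with ICU acquired weakness" (Objective 1) and "To identify differences in accelerometer data that appear only in the ICU acquired weakness group for later use as diagnostic criteria" (Objective 2). Both turn on the contrast between weak and non-weak patients. Neither mentions frequency.

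Section 4 makes frequency a within-subject factor ("Each muscle will be stimulated at three separate stimulation frequencies (2 Hz, 4 Hz, and 6Hz) over 3 minutes each") and adds a second layer: "Each subject will have two target muscle groups tested (extensor carpi radialis longus, and tibialis anterior"). Section 5 gives the only size figure: "Requested Sample Size: 150 (extra 50 to account for subject drop outs").

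**The concern.** Group has two levels, so its main effect needs no follow-up test. The post-hoc step must therefore concern either the frequency levels or the six group-by-frequency cells. Its natural use for Objectives 1 and 2 is to show at which frequency weak and non-weak patients differ. Three contrasts do that. The sentence does not confine the correction to those three, and every further comparison admitted to a Bonferroni family lowers the threshold for them.

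The choice of method is a separate matter. Plain Bonferroni tests every contrast at the strictest threshold. Holm's step-down procedure controls the same error rate under the same conditions and rejects everything that Bonferroni rejects, sometimes more. That holds for any family, however it is defined.

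At stake is the chance of missing a real frequency-specific difference that a later diagnostic study might build on.

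**Working it through.** **The plan's own figures.** The 150 in Section 5 has no alpha, power or effect size behind it, so there is no power calculation to reproduce. Taking off the 50 allowed for dropout leaves 150 - 50 = 100 evaluable.

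**Assumptions, none of them in the documents.** Two-sided family-wise alpha 0.05; a standardised difference d = 0.6; group splits of 50/50 and 30/70 (the split is decided by the MRC score); correlation 0.3 to 0.6 between a patient's values at the three frequencies. Each same-frequency contrast is an independent two-sample comparison within one outcome and one muscle.

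**Step 1: count the comparisons.** 2 groups x 3 frequencies = 6 cells, and 6 x 5 / 2 = 15 pairs. These are:
- 3 weak vs non-weak at the same frequency;
- 2 x 3 = 6 frequency pairs within a group;
- 15 - 3 - 6 = 6 pairs that differ in both group and frequency.

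**Step 2: thresholds.** Bonferroni over 3 gives 0.05/3 = 0.0167. Over 9 (the first two kinds) it gives 0.05/9 = 0.0056. Over all 15 it gives 0.05/15 = 0.0033. Holm over 3 orders the p-values and compares the smallest with 0.05/3, the next with 0.05/2 and the last with 0.05, stopping at the first failure.

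**Step 3: power per contrast by family size.** Noncentral t with 98 degrees of freedom and noncentrality d / sqrt(1/n1 + 1/n2), which is 0.6 / sqrt(1/50 + 1/50) = 3.00 and 0.6 / sqrt(1/30 + 1/70) = 2.75.

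| Split | 3 tests | 9 tests | 15 tests | Loss, 3 to 15 |
|---|---|---|---|---|
| 50/50 | 71.3% | 56.7% | 50.0% | 21 points |
| 30/70 | 62.4% | 46.9% | 40.3% | 22 points |

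The loss depends on the effect. At 50/50 the power with 3 and 15 tests is 34% and 16% for d = 0.4, 94% and 84% for d = 0.8, and 99% and 97% for d = 1.0.

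**Step 4: Holm against Bonferroni over the same three contrasts.** Simulated average power of the truly non-null contrasts, normal approximation (hence the slightly higher Bonferroni values than in Step 3):

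| Contrasts that are real | 50/50, Bonferroni to Holm | 30/70, Bonferroni to Holm | Gain |
|---|---|---|---|
| 3 | 73% to 80-81% | 64% to 71-72% | about 7-8 points |
| 2 | 73% to 76% | 64% to 67% | about 3 points |
| 1 | 73% to 73% | 64% to 64% | about 0.1 points |

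At correlation 0.9, with all three real, the gain is 5-6 points.

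**Step 5: what is left untouched.** The group main effect can be approximated by comparing each patient's mean over the three frequencies, whose SD is sqrt((1 + 2 x rho)/3). With d = 0.6 at every frequency, rho 0.3 to 0.6 and alpha 0.05, power is 98% to 93% at 50/50 and 96% to 89% at 30/70. No Bonferroni correction is stated for this test.

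**The case against.** The strongest reply is that the plan is valid as it stands and that the large loss belongs to a family the plan never names. Much of this stands. The sentence fits three simple effects of group as well as it fits all pairs. A reader might infer from it that every weak vs non-weak contrast will be tested at 0.05/15; Section 6 does not say so, and the 20-point figure is conditional on that reading.

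A reader might go further and conclude that power for the study question is thrown away. The documents do not support that either. The ANOVA comes first, its group main effect is itself the weak vs non-weak test, and its interaction asks whether the group difference varies with frequency. Neither carries a stated Bonferroni correction, and Step 5 shows the main effect well powered in the same scenario.

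It can also be said that neither objective asks for results by frequency, and that a fatigue pattern may include how the response changes across frequencies within a group. That is fair. Limiting the family to three contrasts is a judgement about focus, not something the objectives dictate. Whether such changes differ between groups is, however, an interaction question, which the ANOVA tests and within-group pairs do not. The pairs that mix group and frequency confound the two.

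Finally, Holm's gain is largest when all three contrasts are real, which is also when the main effect is best powered. That too is true and limits the benefit. It does not reverse the direction, since Holm cannot do worse.

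**Conclusion.** The point holds as a minor improvement to the post-hoc step, not as an error. Whatever family is intended, Holm gives the same family-wise control as the named method and is at least as powerful: by about 7-8, 3 or almost 0 points according to whether three, two or one of the contrasts are real. Naming the three same-frequency contrasts also rules out a wider family, which at 15 pairs would cost about 20 points per contrast at d = 0.6 and much less at d = 1.0. All these sizes rest on the assumed alpha, effect, group split and correlation. The overall weak vs non-weak test is unaffected.

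**What to change.** Replace the closing sentence of Section 6 with: *Post-hoc comparisons are weak vs non-weak at 2, 4 and 6 Hz (three contrasts per outcome and muscle), adjusted by Holm's method; within-group frequency comparisons are reported as estimates with intervals.*

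The cost is one sentence, standard software and no extra patients. There are two drawbacks. Holm has no simple matching confidence intervals, so Bonferroni intervals can be shown alongside. Within-group frequency comparisons also become descriptive. Whether to correct across the four outcomes and two muscles (3 x 4 x 2 = 24 tests if all were joined) is a separate question that this change does not settle; the plan should answer it in its own right.
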